8.1 Serious Adverse Events

An SAE is defined as an AE that in the view of either the investigator or the sponsor:

- Results in death
- Is life-threatening, defined as an event in which the subject was, in the judgment of the investigator, at immediate risk of death. This does not include an AE that, had it occurred in a more serious form, might have caused death.
- Requires in-patient hospitalization or prolongation of existing hospitalization
- Results in persistent or significant disability/incapacity
- Is a congenital anomaly/birth defect

In addition, important medical experiences that may not result in death, are not life-threatening, or do not require hospitalization may be considered SAEs when, based upon appropriate medical judgment, they may jeopardize the subject and may require medical or surgical intervention to prevent one of the outcomes listed in the definition. Examples of such medical events include allergic bronchospasm requiring intensive treatment in an emergency room or at home, blood dyscrasias or convulsions that do not result in in-patient hospitalization, or the development of drug dependency or drug abuse.

NOTE: In addition to the above criteria, AEs meeting any of the following criteria, although not SAEs per ICH definition, are reportable to the sponsor in the same timeframe as SAEs to meet certain local requirements:

- New cancer (that is not a condition of the study)
- AE associated with an overdose
- AEs of special interest (refer to Section 8.2)

All subjects with SAEs must be followed up until no further resolution is expected.

8.1.1 Serious versus Severe Adverse Events

To avoid confusion between the terms “serious” and “severe” which have different implications in the context of a clinical study, the following definitions are provided [19]:

The term “severe” is used to describe the intensity (severity) of a specific event (as in mild/grade 1, moderate/grade 2, severe/grade 3, life-threatening/grade 4, and death/grade 5). However, the event itself may be of only minor medical significance (eg, a severe headache). This is not the same as “serious”, which is based on a subject/event outcome or action criteria

associated with events that threaten a subject's life or function. Seriousness (not severity) serves as a guide to the sponsor to determine regulatory reporting obligations.

8.1.2 *Serious Adverse Event Definition Clarifications*

Death is a result of an SAE, and not an SAE itself. The event that, in the investigator's judgment, caused the death is the SAE.

Life-threatening means that the subject was at immediate risk of death from the event as it occurred. Life-threatening does not include an event that might have led to death, had it occurred with greater severity.

In-patient hospitalization means the subjects has been formally admitted to a hospital for a medical cause, for any length of time. This may or may not be overnight. It does not include presentation and care within an emergency department (although an emergency department visit may define a medically important event, which is considered an SAE).

The principal investigator should attempt to establish a diagnosis of an event based on signs, symptoms, and test results or other medical information (when obtained). In such cases, the diagnosis should be documented as the AE rather than the individual signs or symptoms.

8.2 *Adverse Events of Special Interest*

An AE of special interest (serious or non-serious) is one of scientific and medical concern specific to the sponsor's product or program, for which ongoing monitoring and rapid communication by the investigator to the sponsor can be appropriate. Such an event might warrant further investigation in order to characterize and understand it. All AEs of special interest must be reported in a manner similar to SAEs (see Section 8.5.1).

8.2.1 *Adverse Events of Special Interest for Pembrolizumab*

AEs of special interest for pembrolizumab for this study include:

1. An overdose of sponsor's product, as defined in Section 8.2.3, that is not associated with clinical symptoms or abnormal laboratory results
2. An elevated AST or ALT value that is $\geq 3 \times$ ULN and an elevated TBILI value that is $\geq 2 \times$ ULN and, at the same time, an alkaline phosphatase value that $< 2 \times$ ULN, as determined by protocol-specified laboratory testing or unscheduled laboratory testing

NOTE: These criteria are based upon available regulatory guidance documents. The purpose of the criteria is to specify a threshold of abnormal hepatic tests that may require an additional evaluation for an underlying etiology. The study site guidance for assessment and follow-up of these criteria can be made available. It may also be appropriate to conduct additional evaluation for an underlying etiology in the setting of abnormalities of liver blood tests including AST, ALT, TBILI, and alkaline phosphatase that do not meet the criteria noted above. In these cases, the decision to proceed with additional evaluation will be made through consultation between the study investigators

and the sponsor's medical monitor. However, abnormalities of liver blood tests that do not meet the criteria noted above are not AEs of special interest for this study.

8.2.2 Adverse Events of Special Interest and Possible Risks for Tabelecleucel

Tabelecleucel consists of partially HLA-matched, human-derived products using healthy donor PBMCs as starting material. Because of these features, several AEs of special interest (noted in *italics* in this section) will be monitored in this study. *Infusion reactions* and *transmission of infectious disease* can occur with any human-derived product and therefore, such events are considered of special interest. Other T-cell products, specifically chimeric antigen receptor (CAR)-T cells, have been associated with *cytokine release syndrome (CRS)*; though this phenomenon has not been observed in studies with tabelecleucel cell products, this AE is also considered of special interest. Because tabelecleucel is generated from starting material consisting of donor material that includes donor T cells, *GvHD* is also an AE of special interest.

As with any investigational product, there are potential risks associated with tabelecleucel; these risks are listed below for convenience. However, please refer to the current edition of tabelecleucel (ATA129) Investigator's Brochure for further details, including risk mitigation, as well as for up to date risk information.

- Tumor flare reaction
- GvHD
- CRS
- Marrow or organ rejection
- Transmission of CMV infection
- Transmission of other infections
- Infusion-related reactions

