During the Treatment Phase, subjects will receive two 21-day treatment cycles of combination immunotherapy and then undergo a response assessment at the Observation Visit (refer to [Figure 1](#)). Based on the subject's response to the initial 2 cycles s/he may receive one additional consolidation cycle with the same tabelecleucel product or additional treatment cycles with tabelecleucel with the same or a different HLA restriction, if an appropriately matched product is available. Detailed descriptions are provided in [Section 15.2](#). At any time during the Treatment Phase if a subject has a confirmed progressive disease (cPD), it is at the investigator's discretion to continue treatment with tabelecleucel with a different HLA restriction (Switch Therapy), if available without pembrolizumab. A maximum of 4 treatment/consolidation cycles and 1 Switch Therapy, if available will be permitted.

During the Maintenance Phase, subjects will receive tabelecleucel on Day 1 and pembrolizumab on Day 1, Day 21, Day 42, and Day 63 of 84-day maintenance cycles, which will continue until disease progression, unacceptable toxicity, or a total of 35 pembrolizumab infusions (including for treatment, consolidation, and maintenance) have been given. After completing the End-of-Treatment (EOT) Visit 30 days after the last dose of investigational product, subjects will enter quarterly follow-up until 12 months after the last dose of investigational product or until disease progression. During this last phase, survival and disease status will be collected. The end-of-study is defined as the date of the last quarterly follow-up.

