4.7 Subject Replacement

Subjects who discontinue due to a DLT after receiving both pembrolizumab and tabelecleucel during the 21-day DLT assessment window will not be replaced; however, subjects who discontinue due to a DLT associated with the first infusion of pembrolizumab (ie, prior to any tabelecleucel infusion) will be replaced. Subjects who discontinue from Cohort 1 for any reason other than a DLT prior to completing the 21-day DLT assessment window will be replaced until the required number of evaluable subjects complete the 21-day DLT assessment window. Subjects will not be replaced in Cohort 2.

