Myocarditis	Grade 1 or 2	Withhold	Based on severity of AE administer corticosteroids	Ensure adequate evaluation to confirm etiology and/or exclude other causes
	Grade 3 or 4	Permanently discontinue		
All other irAEs	Intolerable/ persistent Grade 2	Withhold	Based on type and severity of AE administer corticosteroids	Ensure adequate evaluation to confirm etiology and/or exclude other causes
	Grade 3	Withhold or discontinue based on the type of event. Events that require discontinuation include and not limited to: Guillain-Barre Syndrome, encephalitis		
	Grade 4 or recurrent Grade 3	Permanently discontinue		

irAEs	Toxicity grade or conditions	Action taken to pembrolizumab ^a	irAE management with corticosteroid and/or other therapies	Monitor and follow-up
Abbreviations: AE: adverse event; ALT: alanine aminotransferase; AST: aspartate aminotransferase; irAE: immune-related AE; IV: intravenous(ly); T1DM: type 1 diabetes mellitus; TBIL: total bilirubin.				
NOTE: For subjects with Grade 3 or Grade 4 immune-related endocrinopathy where withhold of pembrolizumab is required, pembrolizumab may be resumed when AE resolves to grade ≤ 2 and is controlled with hormonal replacement therapy or achieved metabolic control (in case of T1DM).				
^a Withhold or permanently discontinue pembrolizumab is at the discretion of the investigator or treating physician.				

5.2.5.2 *Dose modification and Toxicity Management of Infusion Reactions Related to Pembrolizumab*

Pembrolizumab may cause severe or life-threatening infusion reactions including severe hypersensitivity or anaphylaxis. Signs and symptoms usually develop during or shortly after drug infusion and generally resolve completely within 24 hours of completion of infusion. Dose modification and toxicity management guidelines on pembrolizumab associated infusion reactions are provided in [Table 6](#).

Table 6 Pembrolizumab Infusion Reactions Dose modification and Treatment Guidelines

CTCAE Grade	Treatment	Premedication at Subsequent Dosing
Grade 1 Mild reaction; infusion interruption not indicated; intervention not indicated	Increase monitoring of vital signs as medically indicated until the subject is deemed medically stable in the opinion of the investigator.	None

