  - The above summaries will be repeated for TEAEs that are related or possibly related to study treatment pembrolizumab or tabelecleucel respectively.
- By SOC and PT, sorted by alphabetic order of SOC, then by descending order of PT total frequency
  - Subject incidence of all TEAEs
  - Subject incidence of serious TEAEs
- By PT, sorted by descending order of PT frequency and then by alphabetic order of PT.
  - Subject incidence of TEAEs
  - Subject incidence of serious TEAEs
  - Subject incidence of TEAEs leading to death
  - Subject incidence of TEAEs leading to pembrolizumab or tabelecleucel discontinuation
  - Subject incidence of treatment related TEAEs
  - Subject incidence of treatment related serious TEAEs

- Subject incidence of treatment related TEAEs leading to pembrolizumab or tabelecleucel discontinuation
- By preferred term and worst severity grade
  - Subject incidence of TEAEs
  - Subject incidence of serious TEAEs
  - Subject incidence of treatment related TEAEs
  - Subject incidence of treatment related serious TEAEs
- A summary table of identified and potential risks including TEAEs of special interest (TEAESIs) by PT sorted by risk category and PT in descending order of frequency within a risk category. The Risk categories for tabelecleucel include:
  - infusion-related reactions
  - transmission of infectious disease(s)
  - cytokine release syndrome
  - GvHD event
  - And additional risk of tumor flare.
- A summary table of TEAEs of special interest (TEAESIs) by PT sorted by PT in descending order of frequency for Pembrolizumab include:
  - Overdose- >1000 mg or >/= 5 times the indicated dose
  - Elevated liver values per Pembro label
- A summary table of TEAEs of dose limiting toxicity by PT in descending order of frequency.

The primary cause of all deaths will be summarized.

A listing of all deaths, serious TEAE, and TEAE leading to treatment or study discontinuation, or leading to death will be provided.

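### SAP 11.1 would show pembrolizumab infusion reactions under a tabelecleucel risk heading, and no planned table gives an infusion-reaction rate by product

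*Protocol*

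**What the plan says.** Protocol 8.2.2 explains that tabelecleucel is made from donor cells. It then says that infusion reactions, like transmission of infection, "can occur with any human-derived product and therefore, such events are considered of special interest". The pembrolizumab list in protocol 8.2.1 has two entries: overdose ("An overdose of sponsor's product, as defined in Section 8.2.3, that is not associated with clinical symptoms or abnormal laboratory results") and a liver-test pattern. Infusion reactions are not on it.

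The protocol does recognise that pembrolizumab produces the same kind of event. Section 5.2.5.2 states: "Pembrolizumab may cause severe or life-threatening infusion reactions including severe hypersensitivity or anaphylaxis". Table 6 is given over to managing these reactions.

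SAP 11.1 plans a table of identified and potential risks, including special-interest events, arranged "by PT sorted by risk category and PT in descending order of frequency within a risk category". It continues: "The Risk categories for tabelecleucel include", and the first category listed is infusion-related reactions. A separate pembrolizumab table covers overdose and raised liver values only.

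In the maintenance phase subjects receive "tabelecleucel on Day 1 and pembrolizumab on Day 1, Day 21, Day 42, and Day 63 of 84-day maintenance cycles" (protocol 3.1). Protocol 4.7 also foresees a subject who stops before any tabelecleucel: "subjects who discontinue due to a DLT associated with the first infusion of pembrolizumab (ie, prior to any tabelecleucel infusion) will be replaced".

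**The concern.** The documents name two sources of infusion reactions but give the event a reporting category under only one of them. A risk table headed with one product will be read as describing that product. If its infusion-reaction row is filled from every treatment-emergent event with a matching term, reactions to the antibody appear as reactions to the cell therapy, and a reader of the report cannot see the difference in any table.

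SAP section 1 says the study was terminated at Phase 1B with 12 subjects enrolled, so these subjects are all the safety evidence the study will yield. Protocol 1.3 describes earlier tabelecleucel infusions in nasopharyngeal carcinoma as free of toxicities. Against that background a single misplaced event could make up the whole row.

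**Working it through.** **1. Does a pembrolizumab reaction enter the row?** Following the plan in order:

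- SAP 6.1 defines study treatment as either product or both.
- SAP 11.1 counts events as treatment-emergent from the first dose of study treatment, so a reaction to the first pembrolizumab infusion qualifies.
- SAP 4.1 admits to the Full Analysis Set anyone with one dose of either product and uses that set for all safety analyses. A subject who had only pembrolizumab stays in.
- The risk-table bullet in SAP 11.1 has no condition on relatedness, timing or infused product. Other bullets in the same list are restricted to treatment-related events.

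Nothing in this chain removes the event.

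**2. Does another planned table separate the products?** SAP 11.1 repeats the overall summary for events related to each product, but that summary does not go down to preferred term. The treatment-related tables by preferred term are not split by product. The pembrolizumab special-interest table has no infusion-reaction row. So no planned table gives a product-specific infusion-reaction rate. The data to build one exist: protocol 8.4 has the investigator assess relationship to tabelecleucel or pembrolizumab, and SAP 11.1 lists all adverse events.

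**3. How often is pembrolizumab scheduled alone?** Inputs: 35 pembrolizumab infusions at most; 21-day cycles with one pembrolizumab and three tabelecleucel doses, at most four such cycles; 84-day maintenance cycles with four pembrolizumab doses and one tabelecleucel dose (protocol 3.1, 5.2, 5.2.2). Let t be the number of 21-day cycles.

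The plan's own duration of about 2 years reproduces: 21t + 84(35 − t)/4. For t = 3 this is 63 + 672 = 735 days. For t = 4 it is 84 + 651 = 735 days. 735/365.25 = 2.01 years.

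Maintenance cycles started: 32/4 = 8 for t = 3. For t = 4, 31/4 = 7.75, so again 8.

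| Full course | Pembrolizumab only | Both | Tabelecleucel only | Pembrolizumab-only share of pembrolizumab days |
|---|---|---|---|---|
| t = 3 | 32 − 8 = 24 | 3 + 8 = 11 | 2 × 3 = 6 | 24/35 = 69% |
| t = 4 | 31 − 8 = 23 | 4 + 8 = 12 | 2 × 4 = 8 | 23/35 = 66% |

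For t = 3, as a share of all infusion days: 24/(24 + 11 + 6) = 24/41 = 59%.

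Shorter courses have fewer. Three 21-day cycles plus one maintenance cycle give 3 of 7 pembrolizumab days (43%). A subject who never reaches maintenance has 0 as scheduled, because every pembrolizumab day is then also a tabelecleucel day. Even then a Day 1 reaction can precede tabelecleucel, which is given about an hour later and only if there was no pembrolizumab reaction or the subject has recovered (protocol 6.3.1).

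**4. What does one such subject do to the row?** With 12 subjects, 1/12 = 8.3 percentage points. For scale, 0/12 has an exact 95% interval of 0 to 26.5%, and 1/12 has 0.2 to 38.5%. The SAP plans no intervals for adverse events.

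**5. How likely is it to matter?** The documents give no infusion-reaction rate, so this step uses assumptions. If 3% to 10% of subjects have a pembrolizumab reaction, the chance of at least one among 12 is 1 − 0.97^12 = 31% to 1 − 0.90^12 = 72%. With an assumed 5% tabelecleucel rate and independence, the expected count in the row rises from 12 × 0.05 = 0.60 to between 12 × (1 − 0.97 × 0.95) = 0.94 and 12 × (1 − 0.90 × 0.95) = 1.74.

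**The case against.** The strongest reply is that SAP 11.1 says how the risk table is headed and sorted, but not how an event is assigned to a category. Protocol 8.2.2 ties this special-interest event to the human-derived product, and 5.2.5.2 treats pembrolizumab reactions separately. A programmer who applied 8.2.2 strictly would leave out a reaction on a pembrolizumab-only day. That is possible, but neither document states such a rule, and a table built by preferred term from all treatment-emergent events does not apply one.

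The second reply is that an all-causality count is a sound choice when attribution is open-label and the products are given an hour apart. This stands, and it is why the existing row should be kept. Restricting the table to related events would discard information on a special-interest event.

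Some stronger readings are tempting but not supported:

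- A reader might infer that a primary endpoint is biased upward. The safety endpoint in protocol 3.2 and SAP 3.1 concerns the two products in combination, and the all-causality count is valid for that.
- A reader might infer that pembrolizumab reactions go unreported. They are listed, and causality is collected by product, so with 12 subjects attribution can be recovered.
- A reader might take 59% of infusion days as a misclassification rate. It is the most a full course allows, and it measures opportunity rather than events.
- A reader might conclude that 8.2.1 must gain an infusion-reaction item. The two lists are product-specific and need not match. An addition would bring expedited reporting (protocol 8.2, 8.5.1) in a study already terminated.

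**Conclusion.** The point holds as a fault in one planned table, not in the data or in the combination safety endpoint. Programmed as written, the tabelecleucel risk category would take in any pembrolizumab infusion reaction, and no other planned table would separate the two.

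The size is conditional. It is nil if no pembrolizumab reaction occurs. Otherwise it is 8.3 percentage points for each subject who enters the row for that reason alone, assuming all 12 enrolled subjects were dosed and no unstated allocation rule is applied. The schedule counts assume dosing as planned with neither product withheld. Nothing in the documents shows that a pembrolizumab reaction, or a subject who never received tabelecleucel, actually occurred. No hypothesis test, power figure, DLT rule or dose decision depends on this table.

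**What to change.** In SAP 11.1, keep the all-causality infusion-reaction row, label it as applying to the combination, and add two rows:

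- (a) reactions the investigator rated related or possibly related to tabelecleucel, with onset on or after a tabelecleucel infusion, and with subjects who received tabelecleucel as the denominator;
- (b) reactions rated related or possibly related to pembrolizumab.

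An event attributed to both products appears in both rows, with a footnote giving the number of such events.

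The cost is a short wording change and two table rows, using causality and infusion dates already collected. The downside is small: on days when both products are given, the split rests on open-label investigator judgement. Keeping the combined row beside the other two makes that visible. No change to protocol 8.2.1 is needed.

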8.2.3 Treatment of Overdose

For this study, an overdose of pembrolizumab will be defined as any dose of 1000 mg or ≥ 5 times the indicated dose.

No specific information is available on the treatment of overdose of pembrolizumab. In the event of overdose, the subject should be observed closely for signs of toxicity. Appropriate supportive treatment should be provided if clinically indicated.

8.3 Severity (or Grading) of Adverse Events

The severity of each AE will be determined using a severity grading system, which could be either the CTCAE or the categorical descriptions (mild, moderate, severe, life-threatening, or death); refer to CTCAE version 5 [47]. If the event is listed in the CTCAE tables, the grading scale with clinical descriptions will be used to determine the grade of the event. If the event is not listed in the CTCAE tables, the categorical descriptions will be used, and clinical judgement should be applied to map the severity of the event to the CTCAE grade.

NOTE: the CTCAE system should not be used as a restrictive selection of event terms; ie, the diagnosis term should never be altered to accommodate the CTCAE grade. If the exact term is not listed in the CTCAE, the severity of the event may be based on the closest/similar medical concept from the CTCAE or based on the severity alternative options and mapped to the appropriate CTCAE grade.

For the following AEs, which are not described in the CTCAE, refer to the indicated information for a recommended severity grading system.

- Acute GvHD: refer to Section 15.6.1
- Chronic GvHD: refer to Section 15.6.2

